5.7.1.2 Statistical Analyses

Descriptive statistics (n, mean, SD, % coefficient of variation (%CV), minimum, median, maximum) will be reported for lofexidine concentrations at each time point by treatment. Descriptive statistics (n, mean, SD, % coefficient of variation (%CV), geometric mean, minimum, median, maximum) will be reported for all PK parameters.

The statistical model will be conducted separately for Treatment A versus Treatment B analysis and for Treatment C versus Treatment A analysis using an incomplete block design.

If a subject has immediate pre-dose (0-hour sample) concentrations that are greater than 5% of the measured C_{max} value for that specific study period, the subject's data will be excluded from the statistical analysis. If a subject has measurable pre-dose concentrations that are 5% or less of the measured C_{max} value for that specific study period, the subject's data will be included in the analysis without adjustment.

Linear mixed effect model with treatment, sequence and period as fixed effects and random effects of subject nested within sequence will be used. Sequence effects will be tested against the Type III mean square term for subject-within sequence at the two-sided $\alpha = 10\%$ level of significance. Least squares means for the treatments (LSMEANS statement), the differences between adjusted treatment means, and the standard errors associated with these differences (ESTIMATE statement) will be estimated.

Confidence intervals (90%) on the geometric mean ratios (obtained from logarithmic transformed data) for AUC_{0-t} , $AUC_{0-\infty}$ and C_{max} for the comparison of Treatment A to Treatment B (to compare the test formulation and reference product under fasted conditions) and the comparison of Treatment C to Treatment A (to compare the granules for reconstitution [test formulation] under fed and fasted conditions) will be constructed to test two one-sided hypotheses at the $\alpha = 0.05$ level of significance.⁵⁻⁷

A description of all of the statistical analyses will be provided in the Statistical Analysis Plan (SAP).

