6. ANALYSIS POPULATIONS

6.1 Pharmacokinetic Population

Data from subjects who have sufficient plasma concentrations to characterize C_{max} and AUC_{0-t} of at least one of the study treatments (A, B or C) will be included in the pharmacokinetic analysis. Data from any subject/period that does not provide sufficient plasma concentrations to characterize C_{max} and AUC_{0-t} will be excluded from the pharmacokinetic analysis.

Data from subjects who have sufficient plasma concentrations to characterize C_{max} and AUC_{0-t} from at least two periods of the study, one of which includes Treatment A, will be included in the comparative statistical analysis.

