7.2 Pharmacokinetic and Statistical Analyses

Pharmacokinetic and statistical services will be performed by [REDACTED]
[REDACTED]. SAS[®], Version 9.4 or higher will be used for all pharmacokinetic and statistical calculations.

No concentration estimates will be provided for missing sample values. Any sample with a missing value will be treated as if the sample had not been scheduled for collection. Data from subjects with missing concentration values (such as missing blood draws, lost samples, samples unable to be quantified) may be used if pharmacokinetic parameters can be estimated using the remaining data points, otherwise data from these subjects will be excluded from the final analysis.

Descriptive statistics (n, mean, SD, % coefficient of variation [%CV], minimum, median, maximum, geometric mean, geometric CV) will be reported for lofexidine concentrations at each time point by treatment.

Linear and semi-logarithmic graphs of the concentration-time profiles for each subject will be provided, using the actual times of sample collections. Graphical presentations of mean results will use the scheduled times of sample collections. Actual sample collection time will be used for calculating the pharmacokinetic parameters, although data will be summarized referencing the scheduled sample collection times.

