7.2.1 Pharmacokinetic Parameters

The pharmacokinetic parameters will be determined from the plasma concentration data using a non-compartmental model.

For the test and reference products, the peak exposure (C_{max}) will be the observed maximum plasma concentration; the time to peak exposure (T_{max}) will be the collection time at which C_{max} is first observed.

Areas under the plasma concentration-time curve from time zero to the time of last measurable concentration (AUC_{0-t}) will be calculated by the linear trapezoidal method. Area under the plasma concentration-time curve from time zero to time infinity ($AUC_{0-\infty}$) will be calculated as follows:

$AUC_{0-\infty} = AUC_{0-t} + C_t/\lambda_z$, where C_t is the last measurable plasma concentration and λ_z is the

apparent first-order terminal rate constant.

λ_z will be estimated, when possible, from the negative of the slope of the dataset with the best-fit least-squares linear regression analysis of the terminal ln-linear concentration-time data. The number of data points (3 or more) in the terminal phase (not including C_{max}) to be included in the final regression analysis for an evaluable λ_z will be determined from the dataset that has the highest adjusted R^2 value of 0.7 or more.

λ_z will be considered non-evaluable if (1) the last three terminal points are used to determine λ_z and either the middle or the last point is higher than the preceding point or (2) the resulting adjusted R^2 value is less than 0.7. An evaluable λ_z will be considered not reliable and not reportable if the resulting apparent first-order terminal half-life ($T_{1/2}$) value is longer than the time interval over which λ_z is estimated. If the resulting $T_{1/2}$ value is longer than the time interval over which λ_z is determined, an interval that is longer than the estimated $T_{1/2}$ will be explored. The interval with the next highest adjusted R^2 value will be chosen and the decrease in the adjusted R^2 value will be assessed to determine if a reliable estimation of the λ_z is possible. If λ_z is deemed not reliable then no $T_{1/2}$ and $AUC_{0-\infty}$ values will be reported for that dataset. $T_{1/2}$ will be calculated as $\ln(2)/\lambda_z$.

Apparent volume of distribution during the terminal phase (V_z/F) of the drug from plasma will be calculated as follows: Dose / [$AUC_{0-\infty} \cdot \lambda_z$]).

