9. TABLE, LISTING AND FIGURE SHELLS

The following shells are presented in order to provide a framework for the display of data from this study. These shells may not be reflective of every aspect of this study but are intended to show the general layout of the Tables, Listings and Figures that will be included in the final clinical study report. Tables, Listings, and Figures are numbered following the ICH structure. Table headers, variables names and footnotes will be modified as needed following data analyses. In addition to the standard SDTM datasets; the ADaM datasets; ADSL, ADAE, ADPC and ADPP will be programmed and submitted.

STATISTICAL ANALYSIS PLAN

PROTOCOL No. USWM-LX2-1001 / [REDACTED]

LOFEXIDINE GRANULES FOR RECONSTITUTION (ORAL) FORMULATION, 90 µG/ML

Table 10.1.1 Subject Disposition

Subject Disposition	Overall N = xx
Subjects Randomized	xx (xx.x%)
Subjects included in Safety Population	xx (xx.x%)
Subjects included in Pharmacokinetic Population	xx (xx.x%)
Total Discontinued	xx (xx.x%)
Reason for Discontinuation	xx (xx.x%)
Adverse Event	xx (xx.x%)
Non-Compliance	xx (xx.x%)
Positive Substance Abuse Screen	xx (xx.x%)
Withdrawal by Subject	xx (xx.x%)
...	xx (xx.x%)

Created on: DDMMYYYY

Page 1 of N

STATISTICAL ANALYSIS PLAN

PROTOCOL No. USWM-LX2-1001 / [REDACTED]

LOFEXIDINE GRANULES FOR RECONSTITUTION (ORAL) FORMULATION, 90 µG/ML

Table 11.2.1 Summary of Demographic Data (Safety Population)

		Overall N = xx
Age (years)	Mean \pm SD Range (Min., Max.) Median	xx.x \pm xx.x xx, xx xx
Age Groups	< 18 18 – 40 41 – 64 65 – 75 > 75	x (xx.x%) x (xx.x%) x (xx.x%) x (xx.x%) x (xx.x%)
Sex	Male Female	x (xx.x%) x (xx.x%)
Ethnicity*	Hispanic or Latino Not Hispanic or Latino	x (xx.x%) x (xx.x%)
Race*	American Indian or Alaska Native Asian Black or African American Native Hawaiian or Other Pacific Islander White Multiple	x (xx.x%) x (xx.x%) x (xx.x%) x (xx.x%) x (xx.x%) x (xx.x%)
BMI (kg/m ²)	Mean \pm SD Range (Min., Max.) Median	xx.x \pm xx.x xx, xx xx
Other Factors		
Height (cm)	Mean \pm SD Range (Min., Max.) Median	xx.x \pm xx.x xx, xx xx
Weight (kg)	Mean \pm SD Range (Min., Max.) Median	xx.x \pm xx.x xx, xx xx
Tobacco Users†	Yes No	x (xx.x%) x (xx.x%)

* Categories based on FDA Guidance “Collection of Race and Ethnicity Data in Clinical Trials”, Issue Date: October 26, 2016.

† Defined as current tobacco user (having used tobacco- or nicotine-containing products within 30 days before initial dosing).

STATISTICAL ANALYSIS PLAN

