Like slightly	x (xx.x%)	x (xx.x%)
Neither like nor dislike	x (xx.x%)	x (xx.x%)

STATISTICAL ANALYSIS PLAN

PROTOCOL No. USWM-LX2-1001 / [REDACTED]

LOFEXIDINE GRANULES FOR RECONSTITUTION (ORAL) FORMULATION, 90 µG/ML

	Treatment A N = xx n (%)	Treatment C N = xx n (%)
Dislike slightly	x (xx.x%)	x (xx.x%)
Dislike moderately	x (xx.x%)	x (xx.x%)
Dislike very much	x (xx.x%)	x (xx.x%)

STATISTICAL ANALYSIS PLAN

PROTOCOL No. USWM-LX2-1001 / [REDACTED]

LOFEXIDINE GRANULES FOR RECONSTITUTION (ORAL) FORMULATION, 90 µG/ML

Listing 16.2.1 Discontinued Subjects

Subject No.	Discontinuation Reason	Date of Discontinuation	Time of Discontinuation	Discontinuation Related to COVID-19 Pandemic
xxxx	Withdrawal By Subject	dd/Mmm/yyyy	hh:mm	
xxxx	Withdrawal By Subject	dd/Mmm/yyyy	hh:mm	
...				

Created on: DDMMYYYY

Page 1 of N

Programming Notes: Listings will be presented by subject number. Secondary fields for AEs, PDs, and Other must be listed

STATISTICAL ANALYSIS PLAN

PROTOCOL No. USWM-LX2-1001 / [REDACTED]

LOFEXIDINE GRANULES FOR RECONSTITUTION (ORAL) FORMULATION, 90 µG/ML

Listing 16.2.2 Protocol Deviations

Subject No.	Type of Protocol Deviation	Deviation Date	PD Related to COVID-19 Pandemic
xxxx	Consumption or use of a restricted item	dd/Mmm/yyyy	
xxxx	Assessment performed out of window: Vital signs	dd/Mmm/yyyy	
...			

Created on: DDMMYYYY

Page 1 of N

Programming Note: Secondary fields for deviation categories of Assessment Not Performed and Assessment Performed Out of Window are required to be presented.

STATISTICAL ANALYSIS PLAN

PROTOCOL No. USWM-LX2-1001 / [REDACTED]

LOFEXIDINE GRANULES FOR RECONSTITUTION (ORAL) FORMULATION, 90 µG/ML

Listing 16.2.3 Subjects Excluded from Statistical Analysis

Sub.	Excluded from Analysis	Reason for Exclusion from Analysis	Applicable Treatment(s)
xxxx	A vs B	Subject did not have sufficient pharmacokinetic data for this analysis	B
xxxx	A vs B , C vs A	Pre-dose concentration > 5% of C _{max}	A
xxxx	C vs A	C _{max} observed at first post-dose sampling timepoint	C
xxxx	A vs B, C vs A	Data excluded because of protocol deviation	B, C
...			

Created on: DDMMYYYY

Page 1 of N

STATISTICAL ANALYSIS PLAN

PROTOCOL No. USWM-LX2-1001 / [REDACTED]

LOFEXIDINE GRANULES FOR RECONSTITUTION (ORAL) FORMULATION, 90 µG/ML

Listing 16.2.4.1 Subject Demographics

Subject No.	Sex	Age (yrs)	Ethnicity	Race	Tobacco User	Height (in)	Weight (lbs)	BMI (kg/m ²)
xxxx	Male	43	Not Hispanic or Latino	Black or African American	No	xx	xx	xx.x

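### Do the sample rows in SAP Listing 16.2.3 let subjects be dropped from the primary ratios on grounds that no rule defines?

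*SAP*

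**What the plan says.** The rules for who enters the comparisons stand in the text. SAP 6.1 (matching protocol 5.7.1) takes subjects with enough concentrations to characterise Cmax and AUC0-t "from at least two periods of the study, one of which includes Treatment A, will be included in the comparative statistical analysis". SAP 7.2.1 states that Cmax "will be the observed maximum plasma concentration" and makes no exception for the first sample. SAP 7.2 keeps data with missing samples if the parameters can still be estimated, "otherwise data from these subjects will be excluded from the final analysis". Protocol 5.7.1.2 adds that when the pre-dose concentration exceeds 5% of that period's Cmax, the subject's "data will be excluded from the statistical analysis".

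Listing 16.2.3 then shows four sample rows:

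| Comparison left | Sample reason | Treatment |
|---|---|---|
| A vs B | "Subject did not have sufficient pharmacokinetic data for this analysis" | B |
| A vs B, C vs A | pre-dose above 5% of Cmax | A |
| C vs A | Cmax "observed at first post-dose sampling timepoint" | C |
| A vs B, C vs A | "Data excluded because of protocol deviation" | B, C |

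SAP Section 9 introduces all the shells with this caution: "These shells may not be reflective of every aspect of this study but are intended to show the general layout". It adds that headers, variable names and footnotes will be changed as needed.

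**The concern.** The third and fourth reasons have no counterpart in the operative text. Whether the peak falls at 0.5 h is known only once the concentrations are known, so excluding on it depends on the outcome. The trial is open-label, only the bioanalytical laboratory is said to be blinded, and the SAP is described as final before database lock, not before concentrations are available. Nobody is named to decide exclusions, and no analysis with and without them is planned. If early peaks were commoner under one treatment, dropping those profiles would lower that side of the Cmax ratio. If the subject left the whole comparison, sound AUC values would be lost too. With 16 enrolled to complete 12, one subject can count. The pre-dose rule also seems to differ in scope, with the protocol excluding the subject's data and the listing excluding by comparison and treatment.

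**Working it through.** **1. Match each listed reason to a rule.** Insufficient data matches SAP 6.1 and 7.2. Pre-dose above 5% matches protocol 5.7.1.2. First-sample Cmax and protocol deviation match nothing. Protocol 5.3.3, 5.3.4 and 5.4.1 deal with stopping a subject or a period, not with setting aside data already collected. The factual core of the concern is therefore correct.

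**2. Ask what force a sample row has.** Other rows in the same set cannot be instructions:

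- Listings 16.2.5.1 and 16.2.8.5 show A, B, C in Periods I, II, III, and Listing 16.2.5.2 also puts B in Period II. The four sequences in SAP Section 4 are BAC, BCA, ACB and CAB, so B is only ever in Period I or III.
- Table 11.2.1 has age bands below 18 and above 75. Inclusion is 18 to 50.
- Listing 16.2.4.2 shows ongoing vitamin D. Vitamins within 7 days before dosing are an exclusion.

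These are generic fillers, and the rows of Listing 16.2.3 have the same standing.

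**3. Test the claimed loss of AUC data.** The listing has no column for the parameter. Tables 11.4.1.2 and 11.4.1.3 give the number of subjects separately for AUC0-t, AUC0-∞ and Cmax, so an exclusion confined to Cmax fits the shells. Loss of the AUCs is not shown.

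**4. Test the claimed conflict over the pre-dose rule.** The sample row names Treatment A. A belongs to both comparisons, so losing that profile removes the subject from both. This agrees with the protocol whether its rule means the period or the whole subject.

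**5. Weigh one lost subject.** With period effects p1, p2, p3 and treatment difference τ, the within-subject contrasts are:

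| Sequence | A − B | C − A |
|---|---|---|
| 1 (BAC) | τ + p2 − p1 | τ + p3 − p2 |
| 2 (BCA) | τ + p3 − p1 | τ + p2 − p3 |
| 3 (ACB) | τ + p1 − p3 | τ + p2 − p1 |
| 4 (CAB) | τ + p2 − p3 | τ + p1 − p2 |

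For A vs B with equal sequence sizes, the estimate is the mean of sequences 2 and 3. A subject lost there is 1 of 8 (1 of 6 with 12 completers). The first-sample row, however, concerns C vs A. There the period terms cancel within sequences 1 and 2 and within 3 and 4, so all four sequences contribute and one subject is 1 of 16 (1 of 12).

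Let s² be the variance of a within-subject log-difference. The C vs A variance with 16 subjects is s²/16 = 0.0625 s². With one lost from sequence 2, the pair variances are (1/4)(1/3 + 1/4) = 0.1458 and (1/4)(1/4 + 1/4) = 0.125. Combined, 1/(1/0.1458 + 1/0.125) = 0.0673 s². The standard error rises by √(0.0673/0.0625) − 1, about 4%.

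**6. Bound the bias.** The plan gives no CV and no power calculation, so there is no figure to reproduce. Assume within-subject CVs of 15%, 20% and 30%, paired log-ratios and no period effects, and drop the subject with the highest log-ratio. With s = √(2 ln(1 + CV²)), the mean log-ratio falls on average by E(max)·s/(n − 1), where E(max) is the expected largest of n standard normal values (1.629 for n = 12, 1.766 for n = 16). For CV 20% and n = 12, s = 0.280, the fall is 1.629 × 0.280/11 = 0.0415, and the ratio is multiplied by exp(−0.0415) = 0.959. Simulation of 100,000 trials per case gives the same factors and the chance of a 90% interval within 80–125% at a true ratio of 1.25:

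| CV | n | Factor on ratio | All subjects | Highest dropped |
|---|---|---|---|---|
| 15% | 12 | 0.969 | 5.0% | 14.5% |
| 20% | 12 | 0.959 | 5.0% | 14.3% |
| 30% | 12 | 0.940 | 3.4% | 9.5% |
| 15% | 16 | 0.976 | 5.0% | 13.5% |
| 20% | 16 | 0.968 | 5.0% | 13.8% |
| 30% | 16 | 0.952 | 4.3% | 11.7% |

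This is deliberate selection of the most extreme subject. It bounds the harm from misuse and does not describe a first-sample rule.

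**The case for a change.** The best reply is that calling the listing a shell does not settle the matter. SAP Section 1 promises detail on all remaining aspects of the analysis, and first-sample Cmax is a specific pharmacokinetic criterion, unlike a filler date. Either it is intended and undefined, or it is left over. It cannot comfortably be folded into insufficient data, because the listing shows that as a separate reason. Listing 16.2.2 mixes consumption of a restricted item with vital signs taken out of window, and nothing says which deviations would cost a subject a place in the ratios.

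What stands is that the policy is unwritten, and an exclusion chosen after seeing results could do harm of the size shown above. The direction of bias does not stand. That early peaks favour the solution over the tablet, or the fasted over the fed state, has no source in the documents, and the sample row names the fed treatment. The one timing figure, an anticipated maximum Tmax of about 5 hours in protocol 5.3.4, gives no sign that peaks at 0.5 h are common, though as an upper figure it does not rule them out.

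Striking out both grounds is not a clear gain either. It would hold in the primary ratios a profile after a serious dosing deviation, or a peak that may not have been captured. Statisticians differ on both, so this is a trade-off and not the correction of an error.

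**Conclusion.** No change follows. Two sample reasons in a mock listing lack a written rule. This is a gap in detail that analysts can fill sensibly, because SAP 6.1 governs inclusion and, followed as written, retains every subject with adequate data. The listing itself excludes nobody. If either ground were ever used, Listing 16.2.3 would show the subject, comparison, reason and treatment, so a reader could ask for the ratio both ways.

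One exclusion from C vs A would remove 1 of 16 or 1 of 12 subjects. The worst-case factor of 0.940 to 0.976 rests on assumed CVs and deliberate choice of the extreme subject. The actual frequency and direction cannot be had from the documents. The conclusion takes the SAP's description of its shells at face value. The SAP also cites a Note to File of 08 Feb 2021 that was not available here and may deal with exclusions. The conclusion does not depend on it.

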Appendix 16.1.9 Individual Plasma Lofexidine Concentrations by Subject

Appendix 16.1.9 Individual Plasma Lofexidine Concentrations by Subject – Semi-logarithmic Scale
